10.2.3 Other Outcomes

- 10.2.3.1 Worst clinical status assessed using ordinal scale among participants who become hospitalized. Ordinal scale defined as:
 - Death
 - Hospitalized, on invasive mechanical ventilation or ECMO;
 - Hospitalized, on non-invasive ventilation or high flow oxygen devices;
 - Hospitalized, requiring supplemental oxygen;
 - Hospitalized, not requiring supplemental oxygen (COVID-19 related or otherwise)
- 10.2.3.2 Duration of hospital stay among participants who become hospitalized.
- 10.2.3.3 ICU admission (yes vs no) among participants who become hospitalized.
- 10.2.3.4 Duration of ICU admission among participants who get admitted to the ICU.

10.3 Randomization and Stratification

Eligible participants will be randomized using a 1:1 ratio to each of the study arms using permuted blocks with dynamic institutional balancing to minimize imbalances at any clinical site.

Randomization will be stratified by “high” vs “low” risk of severe disease, where “high” risk is defined by any of the following: age ≥ 60 years, or having any of the following conditions: hypertension, cardiovascular disease, diabetes, chronic kidney disease, chronic liver disease, chronic lung disease or moderate to severe asthma, severe obesity (BMI >40 based on self-report of height and weight), or immunocompromised due to disease or medication.

The study aims to enroll at least 50% of participants in the high-risk stratum. Initially, there will be no restriction on sites to enroll participants in the low-risk stratum. However,

after at least 200 participants have been enrolled, if fewer than 40% of enrolled participants are in the high-risk stratum, then sites may be asked to restrict enrollment to the low-risk stratum, such that, for every five participants they enroll in the low-risk stratum, at least five participants are enrolled to the high-risk stratum.

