10.4 Sample Size and Accrual

The proposed sample size is 2000 participants who take the first (confirmed) dose of study treatment (approximately 1000 per arm). Participants who are randomized but do not take the first (confirmed) dose of study treatment will not be followed and will be replaced.

The study accrual rate will depend on the status of the epidemics at each site, but based on a survey of possible sites is believed to be 100 to 400 participants per week.

- With 100 participants per week the study should fully accrue in 20 weeks
- With 200 participants per week the study should fully accrue in 10 weeks
- With 400 participants per week the study should fully accrue in 5 weeks

The study is designed to evaluate the efficacy of HCQ and Azithro to prevent hospitalizations and death in outpatient adults diagnosed with COVID-19 compared to those receiving placebo. The primary analysis will include testing the null hypothesis of equality of proportions hospitalized/dying in the two randomized arms, and construction of 95% confidence intervals (CIs) for the ratio of proportions between the study arms. The primary analysis will focus on comparing the ratio of proportions because of the uncertainty in knowing what the hospitalization/death rate will be.

With 2000 participants, the study has 90% power to detect a relative reduction of 33.3% in the proportion of participants hospitalized/dying between the study arms (HCQ and Azithro vs. placebo), using the following assumptions:

- Proportion hospitalized/dying in the placebo arm is 15%
- Two-sided test of two proportions with 5% Type I error rate
- Three interim analyses and one final analysis, equally spaced, with stopping guideline determined using the Lan-DeMets spending function approach with an O'Brien and Fleming boundary.
- Allowance for 5% of participants to be lost-to-follow-up prior to being hospitalized or dying.

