10.5 Data and Safety Monitoring

A NIAID-appointed Data and Safety Monitoring Board (DSMB) will undertake reviews of interim data from the study to help ensure the safety of participants in the study, and to recommend changes to the study including termination or modification for safety reasons

or if there is persuasive evidence of efficacy or lack of efficacy of HCQ and Azithro versus placebo in preventing hospitalizations and deaths. The DSMB may also recommend termination or modification of the study if it appears futile on operational grounds to continue the study as designed. The operation of the DSMB is governed by the NIAID DSMB Charter.

To monitor for potential cardiac safety issues, the DSMB will be notified of cases of TdP, ventricular arrhythmias and sudden deaths (with treatment assignment), as the study team becomes aware of them.

At each interim review, the DSMB will review summaries of data by randomized treatment arm for the primary outcome of hospitalization/death, losses to follow-up, adverse events, self-report of treatment cross-over, and the secondary outcomes of death, study treatment discontinuations and associated reasons, duration of symptoms of COVID-19 disease and duration of fever. By-stratum summaries will also be reviewed.

There will be a review of safety data by the DSMB when 250 participants have completed Day 20 of follow-up. Unless otherwise recommended by the DSMB, interim analyses of both safety and efficacy data will occur weekly from when approximately 500 participants have been followed for the primary outcome assessed at Day 20. To allow for the possibility that the proportion of hospitalizations or death is higher than anticipated, the first review of efficacy and safety data may occur earlier, when approximately 62 participants in the two arms combined have been hospitalized or have died (62 is the expected number based on 15% hospitalizations/deaths in the placebo arm and 10% in the HCQ and Azithro arm, with an interim sample size of 500 participants).

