The DSMB will also monitor operational futility. With respect to operational futility, the DSMB may recommend modification or termination of the study if the proportion hospitalized/dying in the control arm is low. In particular, the DSMB might recommend restricting or closing enrollment to the low risk stratum in favor of increasing enrollment to the high-risk stratum. In addition, the DSMB will monitor the loss to follow-up (LTFU) rate. As a benchmark, an overall LTFU rate of more than 10% would be cause for concern. The DSMB should also monitor the treatment cross-over in the placebo arm by participant self-report and, if available, by PK levels of HCQ and Azithro. As a benchmark, a crossover rate of more than 10% in the placebo arm would be a cause for concern.

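### Does the 40% trigger with a five-to-five minimum undercut the aim of at least 50% high-risk participants?

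*Protocol*

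**What the plan says.** Section 10.3 of the protocol states the goal: "The study aims to enroll at least 50% of participants in the high-risk stratum". It starts without any cap: "Initially, there will be no restriction on sites to enroll participants in the low-risk stratum". Once at least 200 participants are enrolled, it adds a conditional step: "if fewer than 40% of enrolled participants are in the high-risk stratum, then sites may be asked to restrict enrollment to the low-risk stratum". The form of the restriction is that "for every five participants they enroll in the low-risk stratum, at least five participants are enrolled to the high-risk stratum".

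Section 10.5 gives a second route. The DSMB may recommend changing or ending the study "if the proportion hospitalized/dying in the control arm is low", and in particular "the DSMB might recommend restricting or closing enrollment to the low risk stratum in favor of increasing enrollment to the high-risk stratum". That route depends on the control-arm event proportion, not on the share of high-risk participants. Section 10.5 also has the DSMB review summaries by stratum, and Section 7.4.2 has the protocol team follow accrual through regular summaries.

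**The concern.** The aim and the rule stand in the same section and do not match.

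- **Dead band.** Between 40% and just under 50% the trial is below its aim, but the rule states no action.
- **No catch-up.** When the rule does apply, its minimum holds later enrolment at 50%. A trial that was below 40% at the trigger and then follows that minimum exactly must finish below 50%.
- **Discretion.** Sites only may be asked, so even a share below 40% does not oblige anyone to act.

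At stake is the case mix. Section 10.5 recognizes that there may be more hospitalizations and deaths in the higher-risk stratum, and Section 10.4 says that power falls if the placebo proportion is below 15%. Too few high-risk participants could therefore mean fewer events than planned.

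**Working it through.** **The plan's own figure.** Section 10.4 gives 90% power for 15% against 10%, two-sided 5%, 2,000 participants, 5% loss to follow-up and four equally spaced looks. With n = 1,000 × 0.95 = 950 per arm and mean proportion 0.125:

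- Standard error under the null: √(2 × 0.125 × 0.875 / 950) = 0.01517.
- Standard error under the alternative: √((0.15 × 0.85 + 0.10 × 0.90) / 950) = 0.01513.
- Power at 5%: Φ((0.05 − 1.960 × 0.01517) / 0.01513) = 91.0%.
- Power at a final nominal level of about 0.043 (my assumption for four O'Brien-Fleming-type looks): 89.9%.

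The stated 90% is reproduced, and no high-risk share enters the calculation.

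**If the rule never triggers.** A steady share *s* gives 2,000 × *s* high-risk participants: 800 at 40%, 900 at 45% and 980 at 49%. All are below 1,000 and all are compatible with the rule.

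**If it triggers and sites keep exactly to the minimum.** Let *t* be the number enrolled at the trigger and *h* the number of those who are high-risk.

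- Final share = (*h* + 0.5 × (2,000 − *t*)) / 2,000
- High-risk per five low-risk needed afterwards to reach 1,000 = 5 × (1,000 − *h*) / ((2,000 − *t*) − (1,000 − *h*))

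| At the trigger | Final share | Needed per five low-risk |
|---|---|---|
| 79 of 200 (39.5%) | (79 + 900) / 2,000 = 48.95% | 5 × 921 / 879 = 5.24 |
| 60 of 200 (30%) | (60 + 900) / 2,000 = 48.0% | 5 × 940 / 860 = 5.47 |
| 195 of 500 (39%) | (195 + 750) / 2,000 = 47.25% | 5 × 805 / 695 = 5.79 |
| 390 of 1,000 (39%) | (390 + 500) / 2,000 = 44.5% | 5 × 610 / 390 = 7.82 |

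For a trigger at 200 with a share of 30% or more, the miss is about one to two percentage points. It grows if the share falls below 40% only late in accrual.

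**Cost of a rule that delivers 50%.** Assume that 40% of eligible presenters are high-risk and that the accrual rate, which Section 10.4 says "is believed to be 100 to 400 participants per week", counts presenters. Then 1,000 / 0.40 = 2,500 presenters are needed instead of 2,000. Accrual takes 25 weeks instead of 20 at 100 per week, 12.5 instead of 10 at 200, and 6.25 instead of 5 at 400. That is 25% longer in each case.

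**The case for a change.** The best case for a change is that control of enrolment belongs in the protocol, that Section 10.3 fixes it in a form that does not deliver its own aim, and that the team is not told whether a final share of 40% to 49% is acceptable. The DSMB route does not settle this, because it answers to the event proportion.

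Power can be brought in by an illustration, on assumptions the protocol does not make. Suppose that 15% is the placebo proportion for a 50:50 mix. At a 40% share it would then lie between 15% (equal rates in the two strata) and 12% (every event in the high-risk stratum, whose rate is then 0.15 / 0.50 = 30%, and 0.40 × 30% = 12%). With a ratio of 0.667, 950 per arm and a two-sided 5% level, power would run from about 91% down to about 83%. Under the same extreme assumption, the 48.95% case gives 0.4895 × 30% = 14.7% and about 90%.

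The description of the rule stands. The rest carries less weight. The lower power figure needs a low-risk stratum with no events at all, and 15% is not tied to any mix in Section 10.4. The quantity that matters for power is the control-arm event proportion, and that is what the DSMB provision in Section 10.5 watches. The share itself is known at enrolment, so the accrual monitoring in Section 7.4.2 can see it drift without waiting for Day 20 data.

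The phrase about restricting enrolment to the low-risk stratum could be read the wrong way round, but the clause that follows fixes its meaning, and Section 10.5 uses the same idiom.

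**Conclusion.** No change follows. Section 10.3 combines a soft target, a lower discretionary trigger and a minimum that sites may exceed. These can coexist, and the section does not promise that the rule will secure 50%. A final share below 50% is compatible with the text: 48.95% or 48.0% for a trigger at 200 with 39.5% or 30%, 47.25% for one at 500 with 39%, and 40% if the share stays there throughout. These figures assume a total of 2,000 and, after a trigger, enrolment at exactly five to five.

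Validity is not affected. Randomization is stratified by risk, and the primary analysis in Section 10.6.1 estimates the effect within each stratum before combining the two. The effect on power cannot be computed from the protocol, which gives no stratum event rates.

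Calling 50% an approximate target would change the wording and no result. Enforcing it would need a higher trigger and a ratio above five to five. On the assumption that 40% of presenters are high-risk, that adds about a quarter to accrual time. Preferring speed to exact case mix, with a DSMB check on the control-arm event proportion, is a fair trade-off that the team can manage during enrolment.

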10.4 Sample Size and Accrual

The proposed sample size is 2000 participants who take the first (confirmed) dose of study treatment (approximately 1000 per arm). Participants who are randomized but do not take the first (confirmed) dose of study treatment will not be followed and will be replaced.

The study accrual rate will depend on the status of the epidemics at each site, but based on a survey of possible sites is believed to be 100 to 400 participants per week.

- With 100 participants per week the study should fully accrue in 20 weeks
- With 200 participants per week the study should fully accrue in 10 weeks
- With 400 participants per week the study should fully accrue in 5 weeks

The study is designed to evaluate the efficacy of HCQ and Azithro to prevent hospitalizations and death in outpatient adults diagnosed with COVID-19 compared to those receiving placebo. The primary analysis will include testing the null hypothesis of equality of proportions hospitalized/dying in the two randomized arms, and construction of 95% confidence intervals (CIs) for the ratio of proportions between the study arms. The primary analysis will focus on comparing the ratio of proportions because of the uncertainty in knowing what the hospitalization/death rate will be.

With 2000 participants, the study has 90% power to detect a relative reduction of 33.3% in the proportion of participants hospitalized/dying between the study arms (HCQ and Azithro vs. placebo), using the following assumptions:

- Proportion hospitalized/dying in the placebo arm is 15%
- Two-sided test of two proportions with 5% Type I error rate
- Three interim analyses and one final analysis, equally spaced, with stopping guideline determined using the Lan-DeMets spending function approach with an O'Brien and Fleming boundary.
- Allowance for 5% of participants to be lost-to-follow-up prior to being hospitalized or dying.

Using this sample size, the following [Figure 10.4-1](#) shows the power to detect effects of different sizes (expressed as the ratio of true proportions hospitalized/dying in the HCQ and Azithro arm vs placebo arm), for a range of true proportions in the placebo arm. The large star indicates the choice of parameters used to design the study: power of 0.9 (i.e., 90%) to detect a true effect size of 33.3% (i.e., 0.667 ratio of proportions) when the true proportion hospitalized/dying in the control arm is 0.15 (i.e., 15%). The power of the study to detect an effect of HCQ and Azithro is reduced if the true ratio of proportions gets closer to 1.0 and/or if the true proportion hospitalized/dying is lower than 0.15.

[figure not shown]

Figure 10.4-1: Treatment/Control Ratio of Proportions Hospitalized/Dying

The following Table 10.4-2 shows the power to detect an effect of the HCQ and Azithro arm accounting for treatment crossover in the placebo arm (i.e., those on the placebo arm who take HCQ and/or Azithro obtained from a source outside the study) for a range of crossover proportions assuming that these participants then experience a 10% hospitalization/death rate. The power is reduced to less than 80% when there is 15% or more crossover in the control arm.

Table 10.4-2: Power to Detect an Effect of the HCQ and Azithro Arm Accounting for Treatment Crossover in the Placebo Arm

Assumed Crossover Proportion In Control Arm	Assumed Hosp/Death Proportion in Control Arm Accounting for Crossover	Power Accounting for Crossover
5%	14.7%	86.4%
10%	14.5%	83.6%
12.5%	14.4%	82.1%
15%	14.2%	78.8%
20%	14%	75.1%

10.5 Data and Safety Monitoring

A NIAID-appointed Data and Safety Monitoring Board (DSMB) will undertake reviews of interim data from the study to help ensure the safety of participants in the study, and to recommend changes to the study including termination or modification for safety reasons

or if there is persuasive evidence of efficacy or lack of efficacy of HCQ and Azithro versus placebo in preventing hospitalizations and deaths. The DSMB may also recommend termination or modification of the study if it appears futile on operational grounds to continue the study as designed. The operation of the DSMB is governed by the NIAID DSMB Charter.

To monitor for potential cardiac safety issues, the DSMB will be notified of cases of TdP, ventricular arrhythmias and sudden deaths (with treatment assignment), as the study team becomes aware of them.

At each interim review, the DSMB will review summaries of data by randomized treatment arm for the primary outcome of hospitalization/death, losses to follow-up, adverse events, self-report of treatment cross-over, and the secondary outcomes of death, study treatment discontinuations and associated reasons, duration of symptoms of COVID-19 disease and duration of fever. By-stratum summaries will also be reviewed.

There will be a review of safety data by the DSMB when 250 participants have completed Day 20 of follow-up. Unless otherwise recommended by the DSMB, interim analyses of both safety and efficacy data will occur weekly from when approximately 500 participants have been followed for the primary outcome assessed at Day 20. To allow for the possibility that the proportion of hospitalizations or death is higher than anticipated, the first review of efficacy and safety data may occur earlier, when approximately 62 participants in the two arms combined have been hospitalized or have died (62 is the expected number based on 15% hospitalizations/deaths in the placebo arm and 10% in the HCQ and Azithro arm, with an interim sample size of 500 participants).

As a stopping guideline for greater efficacy of HCQ and Azithro compared with placebo, the O'Brien and Fleming boundary will be used. Because this spending function is particularly extreme at early interim analyses, a nominal two-sided p-value of <0.001 will instead be used to evaluate early efficacy when a more extreme nominal p-value would be suggested by the O'Brien and Fleming boundary; this has minimal effect on the overall Type I error rate. The stopping guideline will be implemented using the Lan-DeMets spending function approach to allow for the possibility of changes in the timing of interim analyses and/or additional (or fewer) interim analyses if recommended by the DSMB.

In considering possible modifications to the study or termination of the study, the DSMB may consider other outcome measures besides the primary composite hospitalization/death outcome measure, or differences within subgroups. For example, the DSMB might make recommendations based on a high level of evidence for a difference between randomized arms in the proportion dying. Also, for example, recognizing that there may be more hospitalizations/deaths in the higher risk stratum of the study, recommendations might be based on a high level of evidence for a difference in that stratum in the proportion hospitalized/dying or in the proportion dying. In these contexts, a "high level of evidence" might be based on application of the O'Brien and Fleming stopping guideline to the death outcome or the high risk stratum. There is the

possibility that differences between the treatment arms may be observed at an early study time point (for example cumulative proportion at Day 6), however the overall goal of the study is to prevent hospitalization and deaths regardless of the timing, and therefore the focus of the treatment arm comparisons will be at Day 20.

In the absence of a significant difference between randomized arms that leads to termination of the randomized comparison, the study team believes that there is value in continuing the randomized comparison of HCQ and Azithro versus placebo to full enrollment (i.e., 2000 participants) in order to obtain as much precision as possible and to provide maximal information to inform the field.

The DSMB will also monitor operational futility. With respect to operational futility, the DSMB may recommend modification or termination of the study if the proportion hospitalized/dying in the control arm is low. In particular, the DSMB might recommend restricting or closing enrollment to the low risk stratum in favor of increasing enrollment to the high-risk stratum. In addition, the DSMB will monitor the loss to follow-up (LTFU) rate. As a benchmark, an overall LTFU rate of more than 10% would be cause for concern. The DSMB should also monitor the treatment cross-over in the placebo arm by participant self-report and, if available, by PK levels of HCQ and Azithro. As a benchmark, a crossover rate of more than 10% in the placebo arm would be a cause for concern.

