10.6.1 Primary Outcome Measure

The cumulative proportion of participants hospitalized or dying during the first 21 days of follow-up will be estimated for each randomized arm, in each risk stratum, using Kaplan-Meier methods to take account of losses to follow-up. For each stratum, the difference between randomized arms in the estimated log cumulative proportion will be calculated and the variance for this difference will be obtained using Greenwood's formula. To compare the outcome in the overall study

population, the stratum-specific estimated differences in log proportion will be combined across strata, weighted by the inverse of the stratum-specific variance of the difference. Two-sided 95% confidence intervals (adjusted for multiple interim analyses), based on this weighted estimator, and associated p-value for the test of no difference between arms will then be obtained.

Participants who prematurely discontinue the study, who are not able to be contacted by the site to ascertain outcomes after discontinuation, will have follow up censored at the date of last known status.

The above analysis assumes that losses to follow-up are non-informative. As a sensitivity analysis of this assumption, causal inference methods, specifically inverse probability of censoring, may be used. These methods may also be used to evaluate the sensitivity of results to crossover of treatment in the placebo arm (i.e., participants taking HCQ and/or Azithro from sources outside of the study).

To evaluate the potential impact of multiple participants enrolling from the same household on the primary inference an additional sensitivity, analysis will restrict to the first person enrolled from each household. If differences are observed, additional considerations will be given to analyses that account for clustering, for example, bootstrap methods to estimate the variance of difference in the primary outcome between randomized arms.

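### Does the 62-event trigger for an earlier first efficacy review fail to detect a higher-than-anticipated event proportion?

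*Protocol*

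**What the plan says.** Section 10.5 plans weekly interim reviews of efficacy and safety once about 500 participants have been followed to Day 20. It adds an earlier route. "To allow for the possibility that the proportion of hospitalizations or death is higher than anticipated", the first such review may be brought forward to the point "when approximately 62 participants in the two arms combined have been hospitalized or have died". The figure is explained on the spot: it is the expected count at 15% on placebo and 10% on active treatment, "with an interim sample size of 500 participants".

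Three other statements bear on it:

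- Section 10.4 gives accrual that "is believed to be 100 to 400 participants per week" and a look schedule of "Three interim analyses and one final analysis, equally spaced".
- Section 10.5 concludes its remarks on early differences with "therefore the focus of the treatment arm comparisons will be at Day 20". It also asks the board to consider changes "if the proportion hospitalized/dying in the control arm is low".
- Section 10.6.1 fixes the estimand: "The cumulative proportion of participants hospitalized or dying during the first 21 days of follow-up will be estimated for each randomized arm", by Kaplan-Meier.

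**The concern.** The threshold is the expected count at the planned rates, yet its purpose is to catch rates above plan. It is derived from 500 participants with complete follow-up, but the sentence that sets it does not restrict the count to them. Enrolment continues while those 500 complete their 21 days, and later entrants contribute events too. Read literally, the count could reach 62 when the proportion is on plan or below it.

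The board could then be asked to judge efficacy under a rationale that does not apply. With fast accrual it might do so before enough participants had reached Day 20 for the planned comparison to be estimated. It might also seem to clash with the board's task of watching for a low control-arm proportion.

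**Working it through.** **Inputs from the protocol.** Event proportions are 15% and 10% with 1:1 allocation, so 12.5% pooled. The threshold is 62, the interim size 500, accrual 100 to 400 per week and the outcome window 21 days. **Assumption:** the protocol gives no distribution for the day of hospitalization or death, so the mean event day m is varied over 7 (early), 10.5 (uniform) and 14 (late).

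**The protocol's figure.** 250 × 0.15 + 250 × 0.10 = 62.5, which agrees with 62. It is also a quarter of the full-trial expectation: 1000 × 0.15 + 1000 × 0.10 = 250, and 62/250 = 24.8%. That matches the first of four equally spaced analyses.

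**Reading 1: events counted over everyone enrolled.** With r entrants per day, expected events by day t (beyond day 21) are r × 0.125 × (t − m). Setting this to 62.5 gives t = 500/r + m. The 500th participant completes at 500/r + 21. The lead is therefore 21 − m days:

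| Accrual | 500 followed | 62.5 events expected, m = 7 / 10.5 / 14 |
|---|---|---|
| 100/week | day 56.0 | day 42.0 / 45.5 / 49.0 |
| 200/week | day 38.5 | day 24.5 / 28.0 / 31.5 |
| 400/week | day 29.75 | about day 15.8 / 19.2 / 22.8 |

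The lead is 14, 10.5 or 7 days (approximate where t is below 21). In simulation without a reporting lag, the 62nd event came first in roughly 92% to 100% of trials. A 3-day lag shortens each lead by about 3 days.

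When 500 have completed, 3 weeks of entrants are part-way through. With uniform timing they have passed half their risk on average, so the expected total is:

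- 0.125 × (500 + 150) = 81 at 100/week
- 0.125 × (500 + 300) = 100 at 200/week
- 0.125 × (500 + 600) = 138 at 400/week

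For m = 7 to 14, the pooled proportion at which the two triggers coincide is 8.9% to 10.4% at 100/week, 6.9% to 8.9% at 200/week and 4.8% to 6.9% at 400/week. All are below 12.5%, so on this reading the trigger does not single out a high proportion.

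**Reading 2: events counted among followed participants.** The number followed when the 62nd event occurs is negative binomial:

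| Pooled proportion | Median number followed at the 62nd event |
|---|---|
| 12.5% | 494 (middle half 455 to 534) |
| 15% | 411 |
| 18.75% | 329 |
| 25% | 247 |

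The trigger coincides with the 500 mark on plan and moves earlier as the proportion rises, as the sentence intends. The exact chance of at least 62 events in 500 at 12.5% is 0.547. That describes a rule centred on 500, not a false alarm. The lower quartile, 455, is 45 participants short of 500: about 3 days of accrual at 100/week (45/100 × 7) and under a day at 400/week (45/400 × 7).

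**Has nobody completed 21 days at the trigger?** This arises on reading 1, mainly at 400/week. With accrual at full rate from the first day and no lag, nobody has completed in 100% of simulated trials with early timing and about 95% with uniform timing, but only about 5% or fewer with late timing. A 3-day lag takes the uniform case to about 18%; section 6.3.12 allows 72 hours for keying. If accrual instead rises linearly to 400/week over an assumed 2 weeks, the uniform case falls to 0% and the early case to about 31%. With a 3-week rise all three are essentially 0%.

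**Error rates.** A lead of 7 to 14 days means one or two extra weekly looks. Each look held to a nominal p below 0.001 can add at most 0.001 to type I error, so at most 0.002 for two. Power stays about 90%.

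**The case for a change.** The strongest case for a change is that the defect on reading 1 does not depend on event timing. Because m is below 21 the lead is always positive, so a count over everyone enrolled cannot serve its stated purpose, and one clause would cure it. That arithmetic stands. So does the point that Kaplan-Meier cannot estimate the Day 20 proportion when nobody has reached Day 20.

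Three further arguments do not stand.

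- It is not true that both readings fail. The restricted reading behaves as intended and is the one that the derivation of 62 points to.
- The conflict with monitoring for a low control-arm proportion is not real. Nothing tells the board that reaching 62 means rates are high. The trigger sets a date, and at each review the board sees the primary outcome by arm and by stratum.
- The natural replacement is no clear gain. Requiring at least 62 events among the first 400 due for Day 20 would fire in 4.4% of trials at 12.5%, but in only 41% at a pooled 15%. The restricted reading reaches 62 by the 500th participant in about 96% of trials at 15%. Dropping the trigger would remove the early review when rates really are high.

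**Conclusion.** No change is needed. The protocol leaves out a qualifier on which participants the 62 events are counted among, and its own derivation from 500 participants supplies a sensible reading under which the rule works. Under the literal reading the first review could come about 7 to 14 days early at planned rates, less any reporting lag. That range rests on assumed mean event days of 14 to 7. The further worry, that nobody has completed follow-up, needs 400 per week almost from the start, early or uniform event timing and little reporting delay.

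The consequence is small on either reading. The earlier review is optional and the board may recommend another schedule. The Lan-DeMets approach in section 10.5 is adopted so that timing and number of looks can vary, and early looks are held to p below 0.001. Type I error rises by at most 0.001 per extra look, and power and the final analysis are essentially unaffected.
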